### **8.5 Unanticipated Problems**

#### **8.5.1 Definition of Unanticipated Problems (UP)**

Any incident, experience, or outcome that meets all of the following criteria:

- Unexpected in terms of nature, severity, or frequency given (a) the research procedures that are described in the protocol-related documents, such as the Institutional Review Board (IRB)-approved research protocol and informed consent document; and (b) the characteristics of the participant population being studied; and
- Related or possibly related to participation in the research (“possibly related” means there is a reasonable possibility that the incident, experience, or outcome may have been caused by the procedures involved in the research); and
- Suggests that the research places participants or others (which many include research staff, family members or other individuals not directly participating in the research) at a greater risk of harm (including physical, psychological, economic, or social harm) than was previously known or expected.

#### **8.5.2 Unanticipated Problem Reporting**

The investigator will report unanticipated problems (UPs) to the NIH Institutional Review Board (IRB) as per [Policy 801](#).

## 9 STATISTICAL CONSIDERATIONS

### 9.1 Statistical Hypothesis

- Primary Endpoint(s):  $V_T$  of  $[^{11}\text{C}](R)$ -rolipram prior to ketamine infusion compared to  $V_T$  of  $[^{11}\text{C}](R)$ -rolipram after ketamine infusion, within one week. We hypothesize that ketamine infusion will increase rolipram binding similar to that previously described for SSRI treatment.
- Secondary Endpoint(s): We will explore correlations between changes in  $[^{11}\text{C}](R)$ -rolipram binding and clinical rating scales.

### 9.2 Sample Size Determination

The only existing database of patients scanned for PDE4 at baseline and after treatment is the one described by Fujita et al. This work, whose patients were very similar to the ones targeted in this study, analyzed 23 MDD subjects with  $^{11}\text{C}$ -rolipram at baseline and after 8 weeks of antidepressant SSRI treatment. MDD subjects had a ~20% reduction in rolipram binding compared to controls, and the SSRI treatment significantly increased  $^{11}\text{C}$ -rolipram binding by 12% ( $P<0.001$ ). Consequently, we aim at studying a population of the same size as the one that revealed a significant change with pharmacological treatment. Considering dropouts, we wish to recruit up to 35 subjects, with the goal of scanning 23. Correlation/regression analyses will be performed by controlling for possible confounding factors such as age and sex.

### 9.3 Populations for Analyses

Patients with major depressive disorder that qualify for ketamine treatment.

#### 9.3.1 Evaluable for toxicity

No toxicity is expected from the radioligand.

#### 9.3.2 Evaluable for objective response

Participants will be evaluated on the basis of completion of two PET scans as the primary endpoint. Ketamine infusion has been shown to exert an antidepressant effect, which will be evaluated based on changes in clinical rating scales from pre-ketamine baseline, which will then be correlated to change in PET scans.

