### 5 STUDY POPULATION

#### 5.1 Inclusion Criteria

**Patients:** In order to be eligible for this study, MDD participants must meet all of the following criteria:

1. Aged 18 to 70 years old.
2. Female participants of childbearing potential must be using a medically acceptable means of contraception.
3. Participants must be in good general health as evidenced by medical history and physical examination.
4. Each participant must have a level of understanding sufficient to agree to all required tests and examinations and sign an informed consent document.
5. All participants must have undergone a screening assessment under protocol 01-M-0254, “The Evaluation of Patients with Mood and Anxiety Disorders and Healthy Participants”.
6. Participants must be enrolled in the ketamine arms of protocols 19-M-0107 “Ketamine and AMPA”, 17-M-0060 “Neuropharmacology of Ketamine”, or 15-M-0188 “Neurobiology of Suicide”.
7. Participants must fulfill DSM-5 criteria for major depression (MDD) without psychotic features, as based on clinical assessment and structured diagnostic interview (SCID-P).
8. Participants must have an initial score on the MADRS  $\geq 18$  or HAM-D  $\geq 15$  within two weeks of study entry.
9. Participants with stable medical conditions as assessed by their primary care provider (PCP) and/or in-house clinician are permitted to join the study.
10. Patients must qualify for ketamine administration, usually defined as lack of response to two adequate lifetime antidepressant trials, with [at least] one in the current major depressive episode, operationally defined using the Antidepressant Treatment History Form (ATHF); a failed adequate trial of ECT [or TMS] would count as an adequate antidepressant trial.
11. Participants must have their radial artery pulse checked for the presence of adequate ulnar collateral flow and the absence of any metal or foreign objects in both wrists.
12. Participants must agree to adhere to the lifestyle considerations (see Section 5.4).

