### 9.4 Statistical Analyses

#### 9.4.1 General Approach

For the primary endpoint of change in  $[^{11}\text{C}](R)$ -rolipram binding, we will compare the pre-ketamine scans within each subject with their post-ketamine scans using paired sample  $t$ -test.

For the secondary endpoint “Is there a correlation between  $V_T$  and clinical rating scales?”, we will use correlation analyses between the modeling results and the results of the clinical scales.

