#### **9.4.3 Analysis of the Secondary Endpoint(s)**

The outcome measures for the correlative studies will be the VT and the results of the clinical rating scales.

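### The secondary analysis correlates raw symptom change with V_T change and does not name the baseline score as a covariate; adding it costs one degree of freedom and may recover power

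*Combined protocol and SAP*

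**What the plan says.** Section 9.3.2 defines the clinical outcome as "changes in clinical rating scales from pre-ketamine baseline, which will then be correlated to change in PET scans". Section 9.4.1 gives the method only in general terms: "we will use correlation analyses between the modeling results and the results of the clinical scales". Section 9.4.3 starts "The outcome measures for the correlative studies will be the" and goes on to name V_T and the rating-scale results, with no model and no covariates.

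One sentence on adjustment stands in section 9.2: "Correlation/regression analyses will be performed by controlling for possible confounding factors such as age and sex". The list is open-ended. It does not mention baseline severity, and neither does any other analysis section.

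The baseline score is available without new data. The Schedule of Activities (1.3) places the rating scales at Visits 2 and 4, on either side of the infusion. Section 5.1, criterion 8, requires a MADRS of at least 18 or a HAM-D of at least 15 within two weeks of entry.

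The sample size is in section 9.2: "Considering dropouts, we wish to recruit up to 35 subjects, with the goal of scanning 23".

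**The concern.** A change score subtracts the whole baseline value. Unless the post-treatment score tracks baseline point for point, part of the baseline spread stays in the difference. If V_T change is unrelated to baseline severity, that part is noise and pulls the observed correlation towards zero. Regressing the post score on V_T change with the baseline score in the model lets the data set the weight given to baseline.

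This correlation is the only secondary objective in the synopsis and the study's only link between the imaging result and clinical benefit. Section 2.2 reports that in the earlier SSRI study, with 23 rescanned patients, the rise in binding did not correlate with improvement. A null result here should not owe anything to avoidable noise. With 23 pairs there is little power to spare.

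**Working it through.** **The plan's own figure.** There is none for this endpoint. The number 23 is carried over from the SSRI study: "we aim at studying a population of the same size as the one that revealed a significant change with pharmacological treatment". No power or detectable correlation is given for the secondary analysis, so there is nothing to reproduce.

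**Detectable correlation.** Fisher z, two-sided 0.05 (assumed), n = 23, k covariate degrees of freedom:

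power ≈ Φ(√(n − 3 − k) × atanh(r) − 1.96)

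Solving for 80% power gives r = 0.56 with no covariates, 0.58 with age and sex (k = 2), 0.59 with the baseline score added (k = 3), and 0.62 with two protocol terms as well (k = 5).

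**Raw change against baseline adjustment.** All the following inputs are assumed:
- post-score SD s1 = 10
- baseline SD s0 = 5, 7 or 10 (only the ratio s0/s1 matters)
- pre/post correlation ρ = 0 to 0.6
- true baseline-adjusted correlation 0.50
- V_T change independent of the baseline score

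Then

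Var(change) = s0² + s1² − 2ρ·s0·s1

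r_raw = 0.50 × s1·√(1 − ρ²) / √Var(change)

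R² of change on baseline = 1 − (r_raw / 0.50)²

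*Worst case for raw change* (s0 = 10, ρ = 0): Var = 200, so r_raw = 0.50 × 10 / 14.14 = 0.354. Then atanh(0.354) × √20 = 1.65, and power = Φ(1.65 − 1.96) = 38%.

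*A favourable case* (s0 = 5, ρ = 0.4): Var = 85, so r_raw = 0.50 × 9.17 / 9.22 = 0.497, and power = 68%.

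*With the baseline score as the only covariate* (k = 1), in every cell: atanh(0.50) × √19 = 2.39, and power = Φ(2.39 − 1.96) = 67%.

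Power with raw change and no covariates (R² of change on baseline in brackets):

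| Baseline SD | ρ = 0 | ρ = 0.2 | ρ = 0.4 | ρ = 0.6 |
|---|---|---|---|---|
| 5 | 58% (0.20) | 64% (0.09) | 68% (0.01) | 68% (0.02) |
| 7 | 49% (0.33) | 57% (0.21) | 64% (0.10) | 68% (0.02) |
| 10 | 38% (0.50) | 45% (0.40) | 51% (0.30) | 58% (0.20) |

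Adjustment at 67% is higher in nine of the twelve cells and 1 to 2 points lower in three. Break-even is an R² of about 0.05. Simulation over the same grid gives 39% to 71% for raw change and 68% to 70% with baseline alone. The Fisher approximation runs slightly low.

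**With age and sex in both models**, as section 9.2 envisages, the same formulas give 35% to 64% for raw change (k = 2) and 62% with baseline added (k = 3). The pattern is the same: a gain of up to about 27 points and a loss of about 2 at worst.

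**The case against.** **The plan already adjusts.** A reader of sections 9.4.1 and 9.4.3 alone might infer an unadjusted correlation that ignores confounding. Section 9.2 does not support that, and its open-ended wording could take in baseline severity. What stands is narrower: the baseline score is not pre-specified, and an open list leaves the choice until after the data are seen.

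**Raw change need not lose power.** This is correct. The low figure of 39% needs a baseline as variable as the post score and no pre/post correlation. An entry minimum on the MADRS or HAM-D tends to narrow the baseline spread, which favours the cells where raw change does as well or slightly better. A flat statement that the plan loses power is not supported; it may lose power.

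**The independence assumption is borrowed.** Section 2.2 reports that binding did not correlate with baseline severity, but in patients treated with an SSRI. It does not establish that V_T change after ketamine is unrelated to baseline score.

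**Parent protocol.** Because "Participants must be enrolled in the ketamine arms of protocols 19-M-0107" or one of two other studies, a reader might infer that pooling three protocols will create a false link and that a protocol term is essential. The mechanism is possible: section 8.2.2 lets parent-protocol staff do the post-ketamine ratings, and section 1.3 ties procedure timing to other protocols' schedules. The artefact needs protocol to shift both changes, in aligned directions, with participants spread across protocols. Suppose there is no within-protocol link and protocol means differ by 0.5 or 1 SD per step on both variables. The simulated false-positive rate is then 10% or 51% with an 8/8/7 split, but 6% or 14% with 20/2/1, and about 5% with a protocol term. The documents give no split and no difference in population, schedule or response, and section 5.1 applies one set of criteria to all. With baseline, age and sex already in the model, two protocol terms lower power at r = 0.50 from 62% to 57%. A compulsory term is therefore a trade-off, and its omission is not an error.

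**Conclusion.** The point holds as a cheap improvement to a secondary analysis. The plan does not name the baseline score, although it is collected. At n = 23 and a true adjusted correlation of 0.50, naming it as the one added term changes power from between 39% and 71% to about 68% to 70%. That is a gain of up to about 30 points and a loss of 1 to 2 at worst.

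The range rests on assumed SDs and pre/post correlations, a two-sided 5% test, and V_T change independent of baseline severity. Where the truth lies in the range cannot be settled from the documents. The primary paired comparison is untouched, and section 4.2 calls the study exploratory, so the consequence is modest.

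**What to change.** In sections 9.4.1 and 9.4.3, pre-specify the secondary analysis as a linear regression of the post-ketamine score on V_T change, with the Visit 2 score on the same scale, age and sex as covariates. State that V_T change is meant, since these two sections refer only to V_T or the modelling results. Report the V_T coefficient and the partial correlation with 95% confidence intervals, and show the unadjusted correlation beside them.

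Add a sensitivity analysis with parent protocol as a further term, pooling sparsely filled protocols, and a scatter plot marked by protocol.

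The cost is a change of wording and one degree of freedom. With age and sex already in the model, the correlation detectable with 80% power moves from 0.58 to 0.59. If the baseline spread is narrow and the pre/post correlation high, about 1 to 2 points of power are lost. No new data or participants are needed.

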#### 9.3.3 Evaluable Non-Target Disease Response

Participants may exhibit changes in clinical rating scales, in  $[^{11}\text{C}](R)$ -rolipram binding, neither, or both. Correlations will be made to determine if clinical improvement based on ketamine infusion is associated with  $[^{11}\text{C}](R)$ -rolipram binding.

### 9.4 Statistical Analyses

#### 9.4.1 General Approach

For the primary endpoint of change in  $[^{11}\text{C}](R)$ -rolipram binding, we will compare the pre-ketamine scans within each subject with their post-ketamine scans using paired sample  $t$ -test.

For the secondary endpoint “Is there a correlation between  $V_T$  and clinical rating scales?”, we will use correlation analyses between the modeling results and the results of the clinical scales.

#### **9.4.2 Analysis of the Primary Endpoints**

[C](R)-rolipram binding assessed as VT will be compared within subjects with a paired sample *t*-test. VT will be calculated using pharmacokinetic modeling.

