animals. Of the 44 unmedicated MDD patients described above, 23 had a follow-up  $[^{11}\text{C}](R)$ -rolipram scan after approximately eight weeks of treatment with an SSRI [6], which significantly increased  $[^{11}\text{C}](R)$ -rolipram binding (12%,  $p<0.001$ ), with significantly greater increases observed in older patients ( $p<0.0001$ ), although rolipram binding did not correlate with severity of baseline symptoms, and increased  $[^{11}\text{C}](R)$ -rolipram binding during treatment did not correlate with symptom improvement. Taken

**Fig. 3.  $[^{11}\text{C}](R)$ -rolipram signal coincides  $[^{18}\text{F}]$ NaF in McCune Albright Syndrome, demonstrating ability of rolipram to measure cAMP signaling.** Maximum intensity projected images of  $[^{11}\text{C}](R)$ -rolipram of a healthy control and of a patient with MAS, and  $[^{18}\text{F}]$ NaF bone scan from the same patient. The MAS patient shows increased  $[^{11}\text{C}](R)$ -rolipram binding compared to the healthy control, which coincides with areas of fibrous dysplasia as shown on the  $[^{18}\text{F}]$ NaF bone scan. [2]

together, these results elucidate two important and related points. First, the cAMP cascade—as indirectly measured with PDE4 binding—was downregulated in unmedicated patients with MDD. Second, antidepressant treatment normalized this [C](R)-rolipram downregulation. The lack of correlation between PDE4 binding and depressive symptoms could reflect the heterogeneity of the disease and/or the heterogeneity of the target, given that PDE4 has four subtypes. Nevertheless, these results suggest that PDE4 inhibition, perhaps via subtype-selective agents, might again be assessed for efficacy in MDD; the results also broadly support the cAMP theory of depression and of antidepressant action. Our goal in this project is to build on this work to determine if ketamine also targets cAMP signaling similar to SSRI treatment, and if these results correlate to clinical improvements.

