#### **9.4.6 Sub-Group Analyses**

The sample will be analyzed by sex and age, but is too small to be analyzed by other demographic characteristics.

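### Does the primary paired t-test waste precision by leaving age out, when the planning study found larger increases in older patients?

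*Combined protocol and SAP*

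**What the plan says.** The primary analysis is stated twice and consistently. Section 9.4.1: "we will compare the pre-ketamine scans within each subject with their post-ketamine scans using paired sample" t-test. Section 9.4.2: V_T "will be compared within subjects with a paired sample" t-test. Neither mentions a covariate.

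The expected effect comes from the earlier SSRI study. Section 9.1: "We hypothesize that ketamine infusion will increase rolipram binding similar to that previously described for SSRI treatment". Section 9.2 takes its sample size from that study ("we aim at studying a population of the same size as the one that revealed a significant change with pharmacological treatment"), which means 23 people scanned out of at most 35 enrolled, and cites its 12% mean increase with P<0.001. Section 2.2 adds that the increase came "with significantly greater increases observed in older patients", with p<0.0001, but gives no slope, correlation or model.

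Age enters the plan in two other places. Section 9.2 says the correlation and regression analyses will control for factors such as age and sex. Section 9.4.6 says: "The sample will be analyzed by sex and age". It sets no age split or cut-point.

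**The concern.** In a randomised trial, leaving out a baseline variable that strongly predicts the outcome is a known inefficiency, and this plan cites evidence that age is such a variable. Pairing removes the effect of age on the level of V_T but not on its change, so age-related spread in the change stays in the error SD of the t-test. Eligibility runs from 18 to 70, so the spread could be wide.

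The possible gain looks large. If p<0.0001 came from a simple regression on 23 patients, age would explain at least 52% of the variance in change, and regressing the change on age would cut the standard error by about 29%. With a true increase of only 6%, power would seem to rise from 44% to 72% at no cost in scans or participants. It could also be argued that an average change cannot be set against the earlier 12% without accounting for age.

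**Working it through.** **Inputs.** From the documents: 23 completed pairs, a 12% mean increase with P<0.001 in 23 patients, an age effect with p<0.0001, and ages 18 to 70. Assumed because the documents do not state them: two-sided alpha 0.05, ages spread uniformly, and a share R² of the variance in change explained by age. Simulations used 40,000 trials per setting.

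**1. The planned test at the planned effect.** Section 9.2 has no power calculation to reproduce, so the SD of the change is solved from the P-value. Two-sided P=0.001 on 22 degrees of freedom needs t = 3.79. Hence SD ≤ 12 × √23 / 3.79 = 15.2 points, a standardised effect of at least 0.79. Exact noncentral-t power for 12% at n=23 is then at least 95%. Because 15.2 is the largest SD compatible with the P-value, this is a worst case, and so are the powers below.

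**2. How strong age could be.** p=0.0001 on 21 degrees of freedom gives t = 4.78, so r = 4.78 / √(4.78² + 21) = 0.72 and R² = 0.52. This holds only if the result was a subject-level simple regression, which the protocol does not say. R² from 0.1 to 0.52 is a reasonable range.

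**3. Adjusting at the sample mean age.** Regress the change on (age − sample mean age). The intercept equals the mean change exactly, so the estimate is the same as in the paired t-test. Only the standard error differs:

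- paired: 15.18 / √23 = 3.16
- regression, R² = 0.52: 15.18 × √(0.48 × 22/21) / √23 = 2.24

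The same number cannot have two sampling variabilities. Over repeated samples from the patient population, the SD of the mean change in simulation is 3.17, which matches the paired figure. The 2.24 leaves out the variation that arises because the ages in the sample differ from one sample to the next. With a true population-average change of zero, the rejection rates at nominal 5% are:

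| R² | paired t-test | regression centred at sample mean |
|---|---|---|
| 0.3 | 5.0% | about 9.6% |
| 0.52 | about 5% | 16.5% |

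So for the average change, adjustment adds no information and overstates certainty.

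**4. Adjusting at a fixed age.** Centring at an age chosen in advance, such as 44 (the midpoint of 18 to 70), holds the type I error at about 5%. It estimates a different quantity, the change at age 44. The gain to 72% power for a 6% change requires the patients' mean age to equal the chosen age. Otherwise the tested quantity moves by offset × √R² × SD. For patients half an SD older (about 7.5 years, since 52/√12 = 15.0):

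- R² = 0.52: shift = 0.5 × 0.721 × 15.18 = 5.5 points. An average change of 6% becomes 0.5 at the reference age, and 12% becomes 6.5.
- R² = 0.2: shift = 0.5 × 0.447 × 15.18 = 3.4 points. An average of 6% becomes 2.6, and 12% becomes 8.6.

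Chance of declaring an increase:

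| Patients against reference age | R² | True average change | Paired t-test | Fixed-age intercept |
|---|---|---|---|---|
| same mean age | 0.52 | 6% | 44% | 72% |
| 0.25 SD older | 0.52 | 6% | 44% | 27% |
| 0.5 SD older | 0.52 | 6% | 44% | 4% |
| 0.5 SD older | 0.52 | 12% | 95% | 70% |
| 0.5 SD older | 0.2 | 6% | 44% | 12% |
| 0.5 SD older | 0.2 | 12% | 95% | 72% |
| 0.5 SD younger | 0.52 | 0% | 2.5% | about 55% |
| 0.5 SD younger | 0.2 | 0% | 2.5% | about 17% |

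The last two rows are correct statements about people of the reference age, but not about the patients the trial studies. The documents give no expected mean age, so none of these rows can be ruled out.

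**5. Comparison with the earlier 12%.** That figure is itself an average over an age mix that the protocol does not report. A change at age 44 is no easier to compare with it than a plain mean is, and no formal comparison is planned.

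**The case for a change.** The best case for adjustment runs as follows. The plan's own evidence names age as a predictor of the primary outcome, the sample size is borrowed rather than calculated, and a scan within a week of ketamine may show less than eight weeks of an SSRI did. If the effect is near 6%, the t-test has only about 44% power at the largest SD compatible with the earlier P-value, and a regression at a pre-specified age is valid and could do much better. The standard error from sample-mean centring is also legitimate as a conditional statement about people with exactly the ages recruited.

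The facts in this stand, and so does the conditional reading. But the stated question is whether ketamine raises binding in patients with MDD, not in a fixed set of ages or at one age. The intuition from randomised trials does not carry over: there, adjustment removes chance differences in the covariate between arms, whereas here there is no second arm and the age mix belongs to the target. The R² of 0.52 rests on an undescribed model and on an SSRI pattern carrying over to ketamine. At R² of 0.1 to 0.2 the standard error falls only 3% to 8% even in the ideal case, and at R² of zero it rises about 2%.

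A continuous age slope with a confidence interval would be a sensible way to carry out section 9.4.6 and useful for a later study. That is a preference about a supporting analysis whose method the plan leaves open.

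**Conclusion.** The concern does not hold. The unadjusted paired t-test is a valid and suitable analysis of the average within-person change, and it gives up no precision about that quantity. Sample-mean adjustment leaves the estimate unchanged and can push the type I error to about 16.5%. Fixed-age adjustment changes the question and, with an age offset of half an SD, can cut the chance of finding a 12% average increase from 95% to about 70%. At the planned 12% the t-test has at least about 95% power.

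These figures assume two-sided 0.05, 23 completed pairs, an SD of change of at most 15.2 points, uniform ages and R² up to 0.52. That the smaller standard error is not one for the population average follows from the one-group design whenever age matters. Only the size of the error depends on R².
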